The end-of-treatment investigator-reported rate of composite complete remission (CRc) for response evaluable FLT3mut+ subjects receiving gilteritinib 120 mg on Schedule 1 (n=17) was 100%. The CRc rate in FLT3mut+ subjects receiving Schedule 2 induction with daunorubicin was also 100%. Among subjects who received  $\geq 80$  mg/day gilteritinib (n=51), CRc rates for FLT3mut+ subjects were 90.3% (n=28/31).

Response by dose level is outlined below:

Response*	S1 40 mg (N=3)	S1 80 mg (N=1)	S1 120 mg (N=17)	S1 200 mg (N=2)	S1 Total (N=23)	S2 IDR (N=5)	S2 DNR (N=6)
CR n (%)	2 (67%)	1 (100%)	12 (71%)	1 (50%)	16 (70%)	4 (80%)	2 (33%)
CRp n (%)			1 (6%)		1 (4%)		
CRi n (%)	1 (33%)		4 (23%)		5 (22%)	1 (20%)	2 (33%)
CRc ‡ n (%)	3 (100%)	1 (100%)	17 (100%)	1 (50%)	22 (96%)	5 (100%)	4 (67%)
NR/NE n (%)				1 (50%)	1 (4%)		2 (33%)

\*Response parameters were defined according to the International Working Group Criteria for AML (Cheson B, et al. J Clin Oncol. 2003; 12 (24):4642–4649).

‡CRc included patients who achieved CR, CRp, and CRi.

Abbreviations: CR, complete remission; CRc, composite complete remission; CRi, complete remission with incomplete hematologic recovery; CRp, complete remission with incomplete platelet recovery; FLT3, fms-like tyrosine kinase 3; mut+, mutation positive; NR, no response; NE, not evaluable; IDR, Idarubicin; DNR, Daunorubicin.

Grade  $\geq 3$  AEs in  $\geq 10\%$  of patients were febrile neutropenia (63.3%), thrombocytopenia (18.3%), decreased platelet count (16.7%), neutropenia (15.0%), bacteremia (10.0%), sepsis (10.0%), and decreased white blood cell count (10.0%). Serious drug-related AEs in  $>1$  subject were febrile neutropenia (n=9), small intestinal obstruction, lung infection, sepsis, and decreased ejection fraction (all n=2).

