If the Grade  $\geq 3$  laboratory abnormality is not a sign of a disease or syndrome, the abnormality itself should be recorded as an AE or SAE on the eCRF. If the laboratory abnormality can be characterized by a precise clinical term in CTCAE Version 5.0, the clinical term should be recorded as the AE or SAE. For example, an elevated serum potassium level of 7.0 mEq/L should be recorded as "hyperkalemia".

Observations of the same Grade  $\geq 3$  laboratory abnormality from visit to visit should not be repeatedly recorded unless their severity, seriousness, or etiology changes.

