### **7.5.6. Adverse Event**

An overall summary of adverse events by 2 treatment arms will be performed for induction and consolidation separately. It will include number and percentage of treatment-related AE (TrAE), Grade 3 or higher TrAE, serious TrAE, treatment-related grade 3 or higher AE leading to stop treatment and study discontinuation, death, etc. The worst grade of treatment-related non-hematological AE for each patient will also be summarized by treatment arms for induction and consolidation separately.

The following AEs are considered as hematological AEs:

Anemia, CD4 lymphocytes decreased, Lymphocyte count decreased, Neutrophil count decreased, Platelet count decreased, and White blood cell decreased.

All others that are not in the above list will be classified as Non-hematological AEs.

All collected adverse events are coded in MedDRA version 23.0. The treatment-emergent adverse events (TEAE) are defined as database collected AE that onset on or after the first protocol treatment (Gilteritinib or Midostaurin) date or worsening of a pre-existing AE after treatment. TrAE is defined as the investigators' assessed drug-related adverse events and their causality after drug is administered. All TrAE will be summarized by system organ class and preferred term and 2 treatment arms and displayed in frequency order.

All TrAEs that onset before the first dose of consolidation treatment will be summarized in induction tables. The TrAEs that onset on or after the first dose of consolidation treatment will be summarized in consolidation tables.

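### SAP 7.5.6 defines hematological AEs by a closed six-term list, so unlisted cytopenia synonyms and febrile neutropenia dilute the worst-grade non-hematological table

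*SAP*

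**What the plan says.** SAP 7.5.6 (Adverse Event) lists as hematological: "Anemia, CD4 lymphocytes decreased, Lymphocyte count decreased, Neutrophil count decreased, Platelet count decreased, and White blood cell decreased". The next sentence closes the list: "All others that are not in the above list will be classified as Non-hematological AEs". On coding, the section gives the dictionary and nothing more: "All collected adverse events are coded in MedDRA version 23.0". The table that uses the split is described as follows: "The worst grade of treatment-related non-hematological AE for each patient will also be summarized by treatment arms for induction and consolidation separately".

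Neither document gives a synonym group, a rule by system organ class, or a statement on where febrile neutropenia goes. The SAP document history (entry of 3 November 2020) shows that the split was specified on purpose. The table templates are a separate document (SAP 2.1 and 10) and were not available for this check.

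Protocol 8.1 governs recording. With named exceptions, only Grade 3 or higher events and serious events are collected. Where a diagnosis is known, it is recorded in place of symptoms. For Grade 3 or higher laboratory abnormalities that are not part of a disease or syndrome: "If the laboratory abnormality can be characterized by a precise clinical term in CTCAE Version 5.0, the clinical term should be recorded".

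**The concern.** A per-patient worst-grade table restricted to non-hematological events presumably exists to set marrow suppression aside after 7+3, so that other toxicity can be compared between arms. Under the closed list, membership of that table turns on the word that was recorded. A low platelet count entered as *platelet count decreased* stays out, and the same finding entered as *thrombocytopenia* goes in. Febrile neutropenia always goes in.

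Because collection is mostly limited to Grade 3 and above, the scale has few levels left. If the table shows one grade per patient, someone with Grade 3 febrile neutropenia and a Grade 3 liver event looks the same as someone with Grade 3 febrile neutropenia alone. Toxicity in each arm is a stated secondary objective, and the trial is open-label. A regrouping chosen after the results are known would be hard to defend as neutral.

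**Working it through.** The plan states no figure here that can be reproduced. The check applies the SAP rule to the adverse event data in the protocol.

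**1. Do both naming styles occur?** Yes. Protocol 1.3.3 (gilteritinib alone, relapsed or refractory AML) lists thrombocytopenia and a decreased platelet count as separate common events. Protocol 1.3.4 (gilteritinib with induction chemotherapy) does the same, and also lists neutropenia.

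**2. Apply the rule to the Grade 3 or higher terms in Protocol 1.3.4** (any cause, terms seen in at least 10% of patients). I treat reversed word order as the same term.

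| Term | Rate | On the SAP list? | Filed as |
|---|---|---|---|
| Febrile neutropenia | 63.3% | No | Non-hematological |
| Thrombocytopenia | 18.3% | No | Non-hematological |
| Platelet count decreased | 16.7% | Yes | Hematological |
| Neutropenia | 15.0% | No | Non-hematological |
| Bacteremia | 10.0% | No | Non-hematological |
| Sepsis | 10.0% | No | Non-hematological |
| White cell count decreased | 10.0% | Yes | Hematological |

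All seven rates fit a denominator of 60 (38, 11, 10, 9, 6, 6 and 6 patients). The protocol text gives 62 enrolled.

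**3. Share of summed term incidence in the non-hematological class** (events by term, not patients).
- Rule as written: (63.3 + 18.3 + 15.0) / (63.3 + 18.3 + 15.0 + 10.0 + 10.0) = 96.6 / 116.6 = 83% comes from the three neutropenia and thrombocytopenia terms.
- Every plain cytopenia recorded under a listed term, so that only febrile neutropenia enters: 63.3 / (63.3 + 20.0) = 63.3 / 83.3 = 76%.
- Febrile neutropenia set aside, plain cytopenias still entering: (18.3 + 15.0) / (18.3 + 15.0 + 20.0) = 33.3 / 53.3 = 62%.

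**4. Bounds on patients with at least one such event.** The lower bound is the largest single rate. The upper bound is the sum, capped at 100%.
- Rule as written: 63.3% to 100%.
- Plain cytopenias moved out, febrile neutropenia kept: 63.3% to 83.3%.
- Both moved out: 10% to 20%.

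**5. Platelet events.** The share of affected patients found only under the unlisted name is 18.3 / (18.3 + 16.7) = 52% if no patient had both terms. At maximal overlap it falls to (18.3 − 16.7) / 18.3 = 9%.

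**6. Related events.** The SAP table counts treatment-related events only, so steps 2 to 5 cannot be carried over as they stand. Among serious drug-related events seen in more than one subject, febrile neutropenia had 9 cases and four other terms had 2 each: 9 / (9 + 8) = 53%. Nine cases are 9/60 = 15.0% or 9/62 = 14.5% of patients. Related non-serious cases are not reported. If all nine were Grade 3 or higher, the related Grade 3+ rate in that study lay between about 15% and 63.3%.

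**The case against.** The strongest reply is that little is lost. SAP 7.5.6 also tabulates all related events by organ class and preferred term. SAP 7.5.7 summarizes maximum CTCAE grade by laboratory category, and SAP 7.5.9 summarizes ECG change. Protocol 12.2.2 records each patient's maximum grade for each type of toxicity. A reader might infer that the worst-grade table is the plan's only view of organ toxicity, and that a hepatic, gastrointestinal or cardiac difference would be hidden. The documents do not support that; such a difference would be diluted in one table.

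The layout is also unseen. If the table is by term, the unlisted cytopenias are visible rows and mask nothing.

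The CTCAE-term rule in Protocol 8.1 steers isolated laboratory findings, and a list of count-decreased terms is consistent with it. The instruction to prefer a diagnosis does not clearly pull the other way, because thrombocytopenia names the low count and is not an illness behind it. Nothing shows how often sites depart from the rule.

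Where febrile neutropenia belongs is partly convention, and the list was deliberate. The table is descriptive, with no test or stopping rule attached.

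All of this stands as a limit on size. It does not remove the defect. The rule is explicit, both names occur in gilteritinib studies, and a plain cytopenia filed as non-hematological is misfiled under any convention. The CTCAE-term rule concerns laboratory abnormalities and does not settle febrile neutropenia.

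**Conclusion.** The point holds as a classification fault in one descriptive safety table. Plain cytopenias recorded under an unlisted synonym are misfiled, to an extent that depends on recording practice. Febrile neutropenia enters by rule and could account for a large share of the Grade 3 or higher entries.

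The size in this trial is not known. A reader might infer from the phase 1 data that at least 63.3% of patients here would show Grade 3 or higher non-hematological toxicity, in both arms. The documents do not support that. The rate is any-cause, comes from another study whose recording rules are not given, and has no midostaurin counterpart. The 52% for platelet events likewise holds only without patient overlap. Nor do the documents say that nearly all patients have a Grade 3–4 cytopenia recorded as an event; the plain-cytopenia terms in Protocol 1.3.4 run from 10.0% to 18.3%. Leukopenia and pancytopenia are not reported as events anywhere in the documents and are reached only through the catch-all sentence.

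The conclusion rests on the SAP being applied as written, and on the unseen table templates containing no grouping rule of their own.

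**What to change.** Before database lock, replace the six-term list in SAP 7.5.6 with grouped MedDRA preferred terms:
- neutropenia / neutrophil count decreased
- thrombocytopenia / platelet count decreased
- leukopenia / white blood cell count decreased
- lymphopenia / lymphocyte count decreased (CD4 lymphocytes decreased can stay as listed)
- anemia / hemoglobin decreased
- pancytopenia / bone marrow failure

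Report febrile neutropenia as its own row, and give the worst-grade non-hematological table with and without it, so that neither convention has to be argued after the results. State whether the table shows one grade per patient or the worst grade per patient within each term, and align the templates.

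The cost is one SAP paragraph, a term list for programming and one extra table. No new data are needed. SAP 2.1 already provides a running note for changes after finalization. If the database is already locked, record the regrouping in the study report as a deviation and label it post hoc.

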#### **4.4 Patient Randomization**

Patients who then meet eligibility requirements may be randomized for study participation. Patients will be stratified prior to randomization by criteria noted below based on central laboratory assessment of prescreening samples.

Patients will be assigned in 1:1 randomization to Arm A or Arm B (treatment assignments are not blinded):

- TKD vs. ITD FLT3 Mutation
  - If FLT3-ITD Mutation: NPM1 Mutation Status (positive vs. negative)
  - If FLT3-ITD Mutation: Signal Ratio (high [ $\geq 0.5$ ] vs. low [ $<0.5$ ] of FLT3 Wild Type)

Treatment will begin no later than 3 days after randomization.

Full information regarding registration/randomization procedures can be found in the materials provided to study sites. Documentation from the web randomization system including the treatment assignment will be placed in the patient record. Correspondence regarding patient registration/randomization must be kept in the study records.

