As per NCI CTCAE Version 5.0, the term toxicity is defined as adverse events that are classified as either possibly, probably, or definitely related to study treatment. The maximum grade for each type of toxicity will be recorded for each patient, and frequency tables will be reviewed to determine toxicity patterns during induction and consolidation separately by treatment arm.

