### 4.3. Randomization and Blinding

Patients who then meet eligibility requirements may be randomized for study participation. Patients will be stratified prior to randomization by criteria noted below based on central laboratory assessment of prescreening samples.

Patients will be stratified according to FLT3-TKD vs. FLT3-ITD FLT3 mutation. Patients with FLT3-ITD mutation will undergo further stratification with NPM1 mutation status (positive vs. negative) and signal ratio (high  $\geq 0.5$  vs. low  $<0.5$ ) of FLT3 Wild Type). Patients will be randomized to receive standard induction treatment (cytarabine and daunorubicin) with either gilteritinib or midostaurin.

Patients will be assigned in 1:1 randomization to Arm A or Arm B (treatment assignments are not blinded):

- FLT3-TKD vs. FLT3-ITD FLT3 Mutation
  - If FLT3-ITD Mutation: NPM1 Mutation Status (positive vs. negative)
  - If FLT3-ITD Mutation: Signal Ratio (high  $\geq 0.5$  vs. low  $<0.5$ ) of FLT3 Wild Type)

Patients that are negative for FLT3 mutated, will be considered screen failures.

Standard of care induction 7+3 chemotherapy may start prior to randomization while awaiting prescreening test results. Protocol treatment will begin no later than 3 days after randomization.

This is an open-label study. Both patients and investigator know the treatment after the

randomization.

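### Every adverse event table that SAP 7.5.6 spells out is limited to events the unblinded investigator calls drug-related; all-cause tables by arm should be added

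*SAP*

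**What the plan says.** SAP 7.5.6 describes three kinds of adverse event output by arm.

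- **Overall summary.** "It will include number and percentage of treatment-related AE (TrAE), Grade 3 or higher TrAE, serious TrAE, treatment-related grade 3 or higher AE". The list then closes with "AE leading to stop treatment and study discontinuation, death, etc".
- **Worst-grade table.** It covers treatment-related non-hematological events only. Febrile neutropenia is not on the SAP's list of hematological events, so it falls in this table.
- **System organ class and preferred term table.** "All TrAE will be summarized by system organ class and preferred term and 2 treatment arms and displayed in frequency order".

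The rule that assigns events to induction or consolidation is also written for treatment-related events only. The filter is defined as follows: "TrAE is defined as the investigators' assessed drug-related adverse events and their causality after drug is administered". On blinding, SAP 4.3 says: "This is an open-label study"; Protocol 4.4 says the same.

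Protocol 12.2.2 sets the same restriction: "the term toxicity is defined as adverse events that are classified as either possibly, probably, or definitely related to study treatment". Collection is wider. Protocol 8.1 defines an adverse event without regard to causality and requires Grade 3 or higher events and serious events to be recorded. Protocol 8.4 requires serious events and deaths up to 30 days after the last dose, whatever the attribution.

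**The concern.** Randomization supports a comparison of what happened in each arm. It gives less support to a comparison of what was judged drug-related after assignment by someone who knew the assignment. In this trial both arms receive 7+3, which is a ready alternative explanation for many events, so causality is often a matter of opinion.

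The documents also give reasons why that opinion might differ by arm:

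- Gilteritinib is trial-supplied and its identified and potential risks are set out at length (Protocol 11.1). Midostaurin comes from commercial stock and its side effects are left to the package insert (Protocol 11.2).
- A related Grade 3 or higher non-hematological event has different dosing consequences in the two arms (Protocol 6.1.2 and 6.1.3).

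The toxicities of each arm are stated secondary objectives, and the tables will be read side by side. The same event could be counted in one arm and left out in the other, which could create an apparent difference or hide a real one.

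**Working it through.** The plan states no figure on this point, so the first step is textual.

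**1. Which outputs depend on attribution?**

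- Overall summary: every item that is clearly worded is treatment-related. Death is the exception, because the wording leaves open whether all deaths or only related deaths are meant.
- Worst-grade table, organ class and preferred term table, and phase-assignment rule: treatment-related only.
- Treatment-emergent events: defined in SAP 7.5.6, with date rules in SAP 7.2, but used in no table that 7.5.6 describes.
- Laboratory shifts and maximum laboratory grade (SAP 7.5.7), and ECG values and changes (SAP 7.5.9): no attribution needed.
- Overall survival (SAP 7.6.7): death from any cause.
- Missing relatedness is set to related (SAP 7.2), so the filter acts only where a judgement was recorded.

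**2. How much can such a filter remove?** The protocol gives one example, the earlier gilteritinib monotherapy study (Protocol 1.3.3). Any treatment-emergent event: 249/252 = 98.8%. At least one related event: 189/252 = 75.0%. So (249 − 189)/249 = 60/249 = 24.1% of patients with an event would leave a related-only count. This is one arm in a different setting. It shows the size of the filter, not a difference between arms.

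**3. What would unequal attribution do?** Treating one type of event per patient, tabulated rate = all-cause rate × probability that the event is called related. The all-cause rates and attribution probabilities are assumptions. For scale, Grade 3 or higher febrile neutropenia alone was 63.3% with gilteritinib plus chemotherapy (Protocol 1.3.4). With the same all-cause rate in both arms:

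| All-cause rate, both arms | Attribution 65% vs 75% | Attribution 65% vs 85% | Attribution 60% vs 90% |
|---|---|---|---|
| 20% | 13% vs 15% | 13% vs 17% | 12% vs 18% |
| 40% | 26% vs 30% | 26% vs 34% | 24% vs 36% |
| 60% | 39% vs 45% | 39% vs 51% | 36% vs 54% |

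For example, 0.60 × 0.65 = 0.39 and 0.60 × 0.75 = 0.45; 0.60 × 0.60 = 0.36 and 0.60 × 0.90 = 0.54.

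As a yardstick only, since no safety test is planned, take 85 patients per arm (170 at 1:1) and a two-sided 5% Fisher test. In the 60% row the exact probability of a nominally significant difference is 9.7%, 30.5% and 61.3%, against 3.7% when attribution is 75% in both arms.

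**4. Can it hide a difference?** Yes, under the same kind of assumption. All-cause rates of 60% vs 40% would be detected with probability 70.9%. With 75% attribution in both arms the table shows 45% vs 30%, and the probability is 46.0%. With attribution of 60% and 90% respectively the table shows 0.60 × 0.60 = 36% vs 0.40 × 0.90 = 36%, and the probability is 3.3%.

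**The case against.** The strongest defence is that the SAP does what the protocol asks. Protocol 12.2.2 defines toxicity as related events and asks for maximum grades by arm and phase. A reader might infer an SAP-protocol conflict, and there is none. Agreement between the documents does not remove the exposure to attribution, however.

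A reader might also infer that no all-cause table will be produced. The documents do not support that. The table templates are a separate document that was not available, the overall summary ends with an open-ended item, and the rules for assigning treatment-emergent status suggest that it may be used somewhere. What can be said is that SAP 7.5.6 specifies no all-cause event table.

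Three further limits stand. The objectives are two separate descriptions, one per arm, with no safety hypothesis or test. Laboratory toxicities, including liver tests, and QTc are displayed without attribution. And the documents leave open what related refers to: Protocol 8.1 frames attribution around the study drug but then names all four drugs for follow-up. If it covers the whole regimen, an event blamed on 7+3 counts in both arms and the scope for bias shrinks; if it covers only the FLT3 inhibitor, the scope is wider.

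Finally, all-cause tables are not perfect either. Treatment-emergent status starts at the first gilteritinib or midostaurin dose, scheduled for day 8, and consolidation tables include only patients in remission who continue. Randomization fully protects neither, which shapes the fix but does not defeat it.

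**Conclusion.** The point holds as a weakness of a stated analysis rule. Apart from the ambiguous death item, every adverse event table whose content SAP 7.5.6 spells out passes through the causality judgement of an investigator who knows the arm, while all-cause Grade 3 or higher and serious events are already collected. Clinical toxicities such as febrile neutropenia, sepsis and diarrhea are the exposed part.

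A reader might go further and conclude that the toxicity results will be biased, or biased against one drug. The documents support neither: they contain no attribution rates by arm, so direction and size are unknown. The range of 39% vs 45% to 36% vs 54% rests on an assumed common all-cause rate of 60% and assumed attribution probabilities. The primary endpoint and every formally tested result are untouched. This is an inexpensive improvement to the safety reporting.

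**What to change.** In SAP 7.5.6, add tables by arm, split by induction and consolidation, of all-cause:

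- collected Grade 3 or higher events, by system organ class and preferred term and by worst grade;
- serious events;
- events leading to discontinuation;
- deaths, stating explicitly that all causes are counted.

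For induction, count events from the start of on-study collection in Protocol 8.1 (randomization if 7+3 had already begun, otherwise the start of on-study induction), and not only from the first gilteritinib or midostaurin dose. State the denominator to match, since SAP 7.4.1 does not say which drugs count as study medication. Add a note that the consolidation tables describe a subset selected after randomization. Keep the treatment-related tables as the protocol-defined toxicity summary, and say whether related means the FLT3 inhibitor or the whole regimen. If the table templates already contain all-cause displays, name them in 7.5.6.

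The cost is a few extra tables and a short SAP edit. No new data are needed.
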